### **5.3 HDAC6 Inhibition and Ricolinostat**

Histone deacetylases (HDACs) are a family of enzymes that remove acetyl groups from lysine residues on substrate proteins. The function of most HDACs is associated with gene transcription through modification of histone tail acetylation and regulation of chromatin dynamics. However, it has become apparent that some HDACs play a critical role in the regulation and function of lysine acetylation of non-histone proteins in most, if not all, major cellular functions (Choudhary, 2009). In particular, HDAC6 is localized predominantly in the cytoplasm of cells where it is crucial in regulating the stability and function of microtubules (Matsuyama, 2002; Zhang, 2003; Zilberman, 2009; Tapia, 2010; Badding, 2013). Microtubule transport is a crucial component of neuronal survival (Sudo, 2010; Tapia, 2010; Morfini, 2009). HDAC6 activity has been associated with a loss in fast axonal transport, which requires stable microtubules

(d'Ydewalle, 2011; Xu, 2014; Xiong, 2013; Govindarajan, 2013; Dompierre, 2007), and inhibition of HDAC6 with the selective inhibitor Tubastatin A reverses motor neuropathy in a mouse model of type 2 Charcot-Marie-Tooth disease (d'Ydewalle, 2011). These data suggest that inhibition of HDAC6 in peripheral neurons may preserve neuron function and reverse or ameliorate the axonal degeneration observed in peripheral neuropathies such as those common in patients with diabetes.

Ricolinostat is a potent inhibitor of HDAC6 activity (enzymatic IC50 value of 4.7 nM), is 10- to 12-fold less active against Class I HDAC enzymes (HDAC1, 2, 3, and 8), and has minimal activity against Class IIa HDAC enzymes (HDAC4, 5, 7, and 9). HDAC6 is the primary deacetylase enzyme for alpha tubulin (Matsuyama, 2002). Ricolinostat treatment increased the level of acetylated  $\alpha$ -tubulin in primary rat dorsal root ganglion neurons. In a human neuroblastoma cell line, ricolinostat increased the level of acetylated  $\alpha$ -tubulin in a dose-dependent manner.

Neurons are particularly sensitive to disruptions in intracellular transport via the microtubule network. Transport of mitochondria from the cell body to the nerve terminal through the axon (anteriograde transport), as well as transport back to the cell body (retrograde transport), are disrupted in many neurological conditions. Treatment of cultured dorsal root ganglion neurons with high glucose decreases transport in both directions. Pre-Treatment of the cells with ricolinostat prevents the disruption in mitochondrial transport.

Diabetic neuropathic pain is modelled in rats using the streptozotocin (STZ) rat model of tactile allodynia. Rats rendered diabetic by an injection of streptozotocin develop increased sensitivity to otherwise non-painful stimuli (tactile allodynia). Rats with established STZ induced tactile allodynia, as measured by von Frey filament paw withdrawal threshold, treated with ricolinostat showed an immediate restoration of normal paw sensitivity after the first dose. The effect persisted for several days following withdrawal of ricolinostat. The persistence of effect is in contrast with standard of care comparator gabapentin, which reversed tactile allodynia only in the hours following drug administration.

Current treatments for diabetic neuropathic pain are ineffective for the non-painful manifestations of DPN such as numbness and tingling. Mechanism of action studies with HDAC6 inhibitors in chemotherapy-induced neuropathy indicate that ricolinostat has the potential to treat these other symptoms in addition to neuropathic pain. In a mouse model of cisplatin-induced neuropathy, HDAC6 inhibition increased IENFD, reversed numbness, and restored mitochondrial function in peripheral nerves (Krukowski, 2016).

[figure not shown]
#### **5.4 Dose Justification and Clinical Experience**

As described below, a dose of 120 mg ricolinostat administered QD while fasted using a 10 mg/mL oral solution formulation is most likely to demonstrate a treatment benefit vs. placebo in this Phase 2 proof-of-concept study. This dose and dosing regimen selection is based on

pharmacokinetic, pharmacodynamic, and safety data from previous clinical studies, while maintaining appropriate safety margins to exposures achieved in long-term non-clinical toxicology studies.

The pharmacodynamic effects of ricolinostat treatment in humans have been assessed by measurement of concentrations of acetylated  $\alpha$ -tubulin and acetylated histones in circulating peripheral blood monocytes (PBMCs) collected from clinical study patients.  $\alpha$ -tubulin is a substrate for HDAC6 (Matsuyama, 2002) and ricolinostat increases concentrations of acetylated  $\alpha$ -tubulin in PBMCs, multiple myeloma and neuroblastoma cell lines, and dorsal root ganglion neurons in a concentration-dependent manner *in vitro*. Accumulation of acetylated  $\alpha$ -tubulin in PBMCs is therefore considered a proximal marker of intracellular HDAC6 target engagement by ricolinostat (Chang et al, 2007). Histone acetylation is catalyzed by Class 1 HDAC enzymes (eg, HDAC1, 2, 3, and 8) and hence accumulation of acetylated histone represents a marker of off-target pharmacological effects. Data from the 4 completed or ongoing studies in oncology patients demonstrate increases in levels of both acetylated  $\alpha$ -tubulin and acetylated histone following ricolinostat dosing either alone or in combination with other oncology treatments. However, consistent with the selectivity of ricolinostat for HDAC6 over HDAC1, increases in acetylated  $\alpha$ -tubulin are more robust and larger than changes in acetylated histone (Figure 1), suggesting that desired effects on  $\alpha$ -tubulin can be achieved while limiting unwanted effects of histone acetylation. Additionally, the time-course profile of  $\alpha$ -tubulin acetylation mirrors the ricolinostat plasma concentration vs. time profile (Figure 1), suggesting a direct relationship between ricolinostat exposure and its pharmacodynamic effect.

**Figure 1: Ricolinostat Plasma Concentration and Pharmacodynamic Effect vs. Time Profiles Following Ricolinostat Treatment in Combination With Pomalidomide/Dexamethasone**

Source: Study ACE-MM-102

[figure not shown]
VERSION 5.0; 24 September 2021

CONFIDENTIAL

PAGE 23 OF 86

Ricolinostat exposures from dosing with the previous 20 mg/mL oral solution formulation show dose-proportionality up to 160 mg, with an exposure plateau at dose levels  $\geq$  160 mg (Figure 2). Comparative bioavailability data demonstrate that a 120 mg dose of ricolinostat administered using the current 10 mg/mL oral solution formulation provides similar exposures to a 160 mg dose using the previous 12 or 20 mg/mL oral solution formulations (Study ACE-HV-100 and ACE-MM-104). Based on these data, a 120 mg ricolinostat dose has been selected for this study as most likely to provide the highest practically achievable ricolinostat exposure and the maximal achievable pharmacodynamic effect.

**Figure 2: Maximum Observed Plasma Concentrations of Ricolinostat in Patients With Relapsed or Refractory Multiple Myeloma Dosed With Previous 20 mg/ml Oral Solution Formulation**

Ricolinostat alone (open markers) or combination with bortezomib (closed markers). Circles denote first dose (Day 1) and squares repeat dosing (Day 11). Markers represent individual patients and the horizontal bars the geometric mean of the data for each group.

Source: Vogl et al, 2017 (Study ACY-100)

Selection of a once daily dosing regimen and the recommendation to dose while fasted are also based on pharmacodynamic considerations. Ricolinostat is a reversible inhibitor of HDAC6, and the proximal pharmacodynamic effect of acetylation of  $\alpha$ -tubulin in peripheral neurons is expected to correlate with intracellular ricolinostat concentrations. By contrast, downstream pharmacological effects are anticipated to be more long-lived, as the overall acetylation status of  $\alpha$ -tubulin reflects the sum of opposing tubulin acetyl transferase activities: HDAC6-mediated deacetylation is counterbalanced by the acetylation of assembled microtubules by  $\alpha$ -tubulin

N-acetyltransferase 1 (Skultetyova et al, 2017). Even a short-lived decrease in HDAC6 activity is therefore expected to shift the acetylation equilibrium of stable microtubules over a longer time-scale. This is consistent with the results of in vivo pharmacology studies (eg, reversal of paclitaxel-induced neuropathy in rats) where the functional effects of the HDAC6 inhibitors were similar between once- and twice-daily dosing regimens and persisted beyond the end of dosing. On this basis, a QD dosing regimen has been chosen in preference to a twice-daily dosing regimen. With respect to food, although dosing with food appears to have no clinically relevant effect on ricolinostat bioavailability (Study ACE-HV-100), absorption is delayed and peak concentrations are lower. To the degree that pharmacodynamic effects are mediated by maximum plasma concentration ( $C_{max}$ ) as well as area under the concentration curve (AUC), such effects might be smaller if dosed under fed conditions, and therefore ricolinostat will be dosed while fasted.

Clinical safety data from patients with multiple myeloma and healthy volunteers support selection of a 120 mg QD dosing regimen. Clinical data in patients are available from treatment studies of 229 patients assessing ricolinostat's efficacy in multiple myeloma. These data include 15 patients treated with ricolinostat monotherapy at doses up to 360 mg and 214 patients treated with ricolinostat at doses up to 360 mg in combination with several different anti-neoplastic agents. An additional 19 healthy volunteers received up to 3 doses of ricolinostat monotherapy using 2 different formulations in a relative bioavailability/food effect study. The median duration of ricolinostat monotherapy in oncology studies ranged from 1.7 weeks to 12.3 weeks across different dose cohorts, with a maximum duration of therapy of 29.5 weeks in a patient treated with up to 360 mg of ricolinostat daily. Treatment durations in studies of ricolinostat administered in combination with other chemotherapeutic agents have been longer, the longest being 174 weeks in combination with lenalidomide and dexamethasone.

Reviewing the safety data from the monotherapy studies, there did not appear to be a pattern of AEs or laboratory changes attributable to ricolinostat either acutely or during chronic treatment, as the observed AEs and changes in laboratory measures were generally those expected in a population of patients with hematologic malignancies and/or those seen with the oncolytic agents administered in combination with ricolinostat. Similarly, the safety findings in the combination studies did not demonstrate a pattern of AE or laboratory changes suggestive of a ricolinostat-specific serious safety concern. Specifically, there were few AEs among 19 healthy volunteers who received single doses of ricolinostat, while among the 15 patients who received ricolinostat monotherapy at doses up to 360 mg QD, many of the observed AEs were attributed to the underlying disease or intercurrent illness, and there was no clear relationship with dose (Vogl et al, 2017; Study ACY-100). Similarly, safety data from 214 patients who received ricolinostat in combination with other oncology treatments showed no clear dose-related trends in the pattern or incidence of AEs, except that twice daily ricolinostat dosing in combination with bortezomib and dexamethasone was associated with a higher incidence of nausea, vomiting, and diarrhea compared with a QD dosing regimen. The design and results of clinical trials of ricolinostat in combination with anti-neoplastic agents are detailed in the Investigator's

Brochure. Further safety information about ricolinostat is presented in the Investigator's Brochure. Overall the results of these studies do not suggest new concerns or a tolerability profile that would be specific or unsafe in patients with DPN.

The plasma pharmacokinetics of ricolinostat monotherapy are detailed in the Investigator's Brochure. Briefly, ricolinostat is rapidly absorbed (time to maximum plasma concentration ~1 hour) from the gastrointestinal tract, with an apparent plasma elimination half-life of approximately 3 hours. Ricolinostat has been studied in 2 oral formulations, 20 mg/mL and 10 mg/ml. For this study, the 10 mg/mL formulation has been selected for use. With this formulation, ricolinostat plasma exposures plateau at doses above 120 mg, a dose for which exposure ( $C_{max}$  and AUC) is similar to that observed with 160 mg in the previous 20 mg/mL formulation. Ricolinostat exposures at the proposed 120 mg clinical dosing regimen using the 10 mg/mL formulation are comparable to exposures associated with efficacy in non-clinical pharmacology studies. Peak plasma exposures from 120 mg QD dosing while fasted are expected to be approximately 600 ng/mL, corresponding to unbound exposures of approximately 150 nM. By comparison, ricolinostat inhibits HDAC6 in vitro with an  $IC_{50}$  of 5.7 nM and average peak exposures from 30 mg/kg dosing in rats were <500 ng/mL.

**Table 2: Exposures in Humans Relative to Highest Exposures Observed in Rat and Dog Chronic Toxicology Studies**

	$C_{max}$ (mean [RSD] ng/mL)		$AUC_{\infty}$ (mean [RSD] hr*ng/mL)	
Human exposure (120 mg)	609 (38%)			962 (30%)
Rat (Day 180) (60 mg/kg)	Male	Female	Male	Female
	662 (+)	1069 (+)	2693 (+)	1736 (+)
Dog (Day 271) (30 mg/kg)	Male	Female	Male	Female
	7155 (40%)	4873 (33%)	18839 (34%)	13459 (33%)

+ RSD not calculated.

Source: Ricolinostat (ACY-1215) Investigator's Brochure, section 3.3.2.2 for chronic toxicology study details

Taken together, the available evidence suggests that a 120 mg dose will provide sufficient exposure to allow an informative test of the hypothesis that HDAC6 inhibition can ameliorate the symptoms of painful DPN while maintaining a favorable safety and tolerability profile based on acute and chronic non-clinical toxicology studies and previous human experience.

## 5.5 Study Design Rationale

The study described here is a Phase 2 proof-of-concept investigation of the efficacy of ricolinostat for the treatment of diabetic neuropathic pain. As noted above, ricolinostat is a potent inhibitor of HDAC6 enzyme activity and represents a promising novel approach to the treatment of diabetic neuropathic pain. As described above and in the Investigator's Brochure, preclinical data from animal models suggest that ricolinostat may offer advantages over currently available

therapies with respect to magnitude of effect, duration of effect, and/or tolerability. Because pain is measured subjectively, it can be subject to expectation bias or other non-specific effects, and in order to accurately assess the efficacy of interventions, it is important to control for this. For this reason, this study is designed as double-blind and placebo-controlled. The use of placebo rather than active comparator is required to provide a definitive understanding of whether observed improvement is or is not treatment-specific, and is justified on scientific and ethical grounds, as 1) there is no convincing evidence that the active treatments currently available to patients change the course of the disease, and thus patients are not put at risk for disease worsening or long-term harm by not administering currently available active treatments for limited periods; 2) rescue medication for acute episodes of pain is permitted in this protocol to ensure that patients are not at risk for excessive discomfort; and 3) per protocol, one medication that patients have been taking to treat their pain for at least 3 months at the time of Screening can be continued during the study provided the regimen has been stable and is expected to remain stable during the study.

## **6.0 STUDY OBJECTIVES**

### **6.1 Primary and Key Secondary Objectives**

- The primary objective of this study is to evaluate the safety and efficacy of ricolinostat compared with placebo for painful DPN as measured by an 11-point NRS after 12 weeks.
- Key secondary objectives include 1) evaluating the efficacy of ricolinostat at 4 weeks as assessed by NRS and 2) evaluating the efficacy of ricolinostat in improving non-pain neuropathic signs after 12 weeks as assessed by change in the UENS.

### **6.2 Secondary Objective**

The secondary objective of this study are to assess the efficacy of ricolinostat for non-pain diabetic peripheral neuropathic signs and to further assess efficacy in painful DPN.

### **6.3 Exploratory Objectives**

The exploratory objectives of this study are to assess the effects of ricolinostat on IENFD, a potential biomarker for efficacy, at 24 weeks in a subset of patients with painful DPN who have reduced IENFD at baseline.

## **7.0 INVESTIGATIONAL PLAN**

### **7.1 Overall Study Design and Plan Description**

This is a randomized, double-blind, 2-arm, parallel group study of up to 274 evaluable patients designed to evaluate the safety and efficacy of ricolinostat for painful DPN.

After signing the ICF and agreeing to participate, initial eligibility assessments will be completed during a Screening visit scheduled between 45 and 14 days prior to planned randomization. Patients may continue one permitted medication for painful DPN if they have been taking it for at least 3 months prior to Screening, provided that the regimen and dose have been stable for at least 3 months prior to Screening and are expected to remain unchanged for the duration of the study. If any pain medication is stopped during the Screening period, then prior to proceeding to the Pain Observation Period:

1. The Investigator must document that there has not been a 'rebound flare,' or that if such a flare has occurred, it has resolved.
2. The Investigator must document that a steady state pain baseline is present.
3. A minimum period of time equal to at least 5 half-lives of the drug in question must pass.

Prior to randomization, patients will participate in a baseline Pain Observation period from Day -14 to Day -1, during which the NRS (average and worst pain) will be recorded daily using an electronic daily diary that will be completed by patients to allow patients to familiarize themselves with the pain rating procedures along with initiation of daily placebo dosing. During the Pain Observation period and thereafter during the study, patients will be allowed to use acetaminophen as rescue pain medication at a maximum dose of 500 mg at 6-hour intervals up to 4 times in any given 24-hour period. Patients will record the pain assessments and any rescue medication use. A follow-up phone contact will be conducted at Day -7 to Day -5 to review diary and dosing compliance.

At the end of the Pain Observation period, patients whose diary compliance, overall level of pain, and pain variability, along with placebo dosing meet entry criteria, will be randomized in a 1:1 ratio to receive either ricolinostat or placebo.

Pre-Treatment assessments will be completed as outlined in [Table 1](#). The first dose of study drug will be given in the clinic and a 12-lead ECG will be performed 1-hour post-dose.

[figure not shown]
During the 12-week randomized, double-blind, placebo-controlled Treatment period, patients will return for assessments as per the schedule of assessments shown in [Table 1](#). An electronic daily diary will be completed by patients to record study and rescue medication (acetaminophen) use, as well as NRS pain assessments. Rescue medication (as needed) and one permitted medication that has been used at a stable dose for at least 3 months prior to starting the Pain Observation period may be used during the study. Other pain medications are prohibited during the Treatment period. Diary data will be reviewed with the patient at each study visit to determine if further instruction is required and to document any discrepancies with study drug or rescue medication dosing.

At the conclusion of the approximately 12-week double-blind, placebo-controlled Treatment period, patients will enter an approximately 12-week open label Safety Extension period during which all patients will receive ricolinostat 120 mg daily and complete evaluations and clinic visits as per the schedule of events. At the conclusion of the Safety Extension, there will be an approximately 4-week washout and Safety Follow-up period, which will incorporate 2 visits at approximately 2 and 4 weeks following the final Safety Extension visit, with assessments performed as outlined in the schedule of assessments ([Table 1](#)).

IENFD will be studied in approximately 120 patients at a selected subgroup of investigational centers by skin biopsy during the baseline observation period and again at the end of the approximately 24 week treatment period. At each timepoint, two samples will be taken from each patient: one proximally on the lateral thigh 10 cm above the fibular head, and one distally towards the ankle 10 cm above the lateral malleolus. This sub-study will include at least 60 patients randomized to the ricolinostat group and a similar number of patients randomized to the placebo group. Based on 1:1 randomization to the study treatment arms, among 24 week completers, approximately half the sample of patients participating in the IENFD sub-study will have 24 weeks of exposure to ricolinostat and approximately half will have 12 weeks of exposure to ricolinostat, providing an opportunity to assess magnitude of change as well as time course of change in IENFD. This sub-study is exploratory and the null hypothesis of greatest interest is that the change from baseline in nerve fiber density is zero in the group receiving 6 months of ricolinostat. The power of this sample size to detect an effect is not known precisely. However, extrapolating from rates of nerve fiber regrowth in healthy subjects after capsaicin administration, assuming a moderate drug effect, and even assuming a slower rate of regeneration as compared with healthy subjects, the proposed sample is expected to provide approximately 80% power to detect an increase of 0.44 fiber/mm assuming a standard deviation of 1.2 fibers after 24 weeks of treatment. Because nerve fiber density may decrease with age, patients older than 75 years are not eligible to participate in the intraepidermal nerve fiber biopsy sub-study. To mitigate the risk that more than a simple ‘band-aid’ type dressing would be required after the biopsy, patients taking anticoagulants are not eligible for intraepidermal nerve fiber biopsy.

A study flow diagram is presented in [Figure 3](#).

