#### **10.3.6 Exploratory Efficacy Outcome Measures**

The exploratory endpoint of change in IENFD from baseline to Week 24 will be analyzed in a subgroup of approximately 120 patients at selected sites. There are 3 comparisons of interest for this analysis:

1. Change from baseline in the IENFD in the group of approximately 60 patients that received ricolinostat for 24 weeks.
2. Change from baseline in the IENFD in the group of approximately 60 patients that received ricolinostat for 12 weeks.
3. The difference in the change from baseline in the IENFD in the Intent-to-Treat population.

For the first two comparisons, an ANCOVA model with baseline density will be fit and the test of difference will be based on the significance level of the intercept term in the model. For the third comparison, an ANCOVA model with baseline density and treatment group as covariates will be used to calculate the nominal p-value.

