#### 4.3.4. *Exploratory endpoints*

The exploratory endpoints for this study are:

- Change in intraepidermal nerve fiber density (IENFD) from baseline to Week 24 will be analyzed in a subgroup of approximately 120 patients at selected sites. Note that placebo subjects will have received ricolinostat for 12 weeks, while treated subjects will have received ricolinostat for 24 weeks. There are 4 comparisons of interest for this analysis:
  - Change from baseline in the IENFD in the group of approximately 60 patients that received ricolinostat for 24 weeks.
  - Change from baseline in the IENFD in the group of approximately 60 patients that received ricolinostat for 12 weeks.
  - The difference in the change from baseline in the IENFD in the Intent-to-Treat population at Week 24.
- Other exploratory endpoints may be identified at the time of analysis of the study data.

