## 10. Exploratory analyses

The exploratory endpoints for this study and a description of the analysis approach for each endpoint are provided below. Change in intraepidermal nerve fiber density (IENFD) from baseline to Week 12 and Week 24 will be analyzed in a subgroup of approximately 120 patients at selected sites. There are 4 comparisons of interest for this analysis:

- Change from baseline in the IENFD in the group of approximately 60 patients that received ricolinostat for 24 weeks. The change from baseline in IENFD will be assessed at 24 weeks using a t-test to test the null hypothesis that the change from baseline in IENFD is zero.
- Change from baseline in the IENFD in the group of approximately 60 patients that received ricolinostat for 12 weeks. The change from baseline in IENFD will be assessed at 12 weeks using a t-test to test the null hypothesis that the change from baseline in IENFD is zero. .
- The difference in the change from baseline in the IENFD in the Intent-to-Treat population at Week 24. An ANCOVA model with change from baseline as the outcome and baseline value and treatment group will be used to test for a difference in groups.
- Other exploratory endpoints may be identified at the time of analysis of the study data.

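### The lead nerve fibre density test is a before-and-after test in the ricolinostat arm alone; the stated 80% power belongs only to that test, and SAP Section 10 plans a Week 12 test with no Week 12 biopsy

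*Protocol*

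**What the plan says.** Protocol Section 7.1 sets the size: "This sub-study will include at least 60 patients randomized to the ricolinostat group and a similar number of patients randomized to the placebo group". It calls the sub-study exploratory, admits that its power is not known precisely, and names its lead hypothesis: "null hypothesis of greatest interest is that the change from baseline in nerve fiber density is zero in the group receiving 6 months" (the group meant is the arm randomised to ricolinostat). It then expects the sample to give "approximately 80% power to detect an increase of 0.44 fiber/mm assuming a standard deviation of 1.2 fibers after 24 weeks of treatment".

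SAP Section 10 lists the tests:

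- **24-week ricolinostat group:** "The change from baseline in IENFD will be assessed at 24 weeks using a t-test to test the null hypothesis" of zero change.
- **Placebo-start group:** the same kind of t-test, but of the change at 12 weeks.
- **Between arms:** "The difference in the change from baseline in the IENFD in the Intent-to-Treat population at Week 24", by ANCOVA with baseline density and treatment group. No power is given for this comparison in either document.

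All patients take ricolinostat from Week 12, and SAP Section 4.3.4 notes that "placebo subjects will have received ricolinostat for 12 weeks, while treated subjects will have received ricolinostat for 24 weeks". Both schedules of assessments place the biopsies at Day 1 and Week 24 only. The one exception is an early-termination biopsy during the extension. SAP Section 4.3.4 defines the endpoint as change to Week 24, whereas SAP Section 10 opens with change to Week 12 and Week 24.

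**The concern.** The sub-study has a randomised control, but its lead test does not use it. Any change that both arms share over 24 weeks (assay or reader drift, natural progression, altered glycaemic control) is counted as drug effect if upward and hides a drug effect if downward. Protocol Section 7.2 justifies placebo for the pain endpoint because uncontrolled improvement cannot be read as treatment-specific. The same logic applies here.

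Protocol Section 10.2.1.3 hopes the biopsies will help to assess whether ricolinostat has structural effects on nerves, and Section 7.2 treats IENFD as a possible biomarker of efficacy. A misread within-arm p-value could therefore influence later development. A reader may also attach the 80% to the randomised sub-study as a whole, although the comparison that uses the randomisation has much less power.

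**Working it through.** **Inputs.** Increase 0.44 fibers/mm, SD 1.2 and 60 per arm (Protocol Section 7.1). Two-sided 0.05 (the general rule in SAP Section 6.1.3). The protocol does not say whether 1.2 is the SD of change or of a single reading. I read it as the SD of change, which reproduces the stated power. If it were a single-reading SD, the same result would need a correlation of about 0.5 between the two biopsies.

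**Method.** Power = P(|T| > t critical), with T noncentral t.

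**1. The plan's figure: one-sample test, n = 60.** SE = 1.2/√60 = 0.155. Noncentrality = 0.44/0.155 = 2.84, df 59. Power = **79.8%**, so the stated 80% is reproduced, provided all 60 contribute a Week 24 biopsy. A two-sample test with these inputs does not give 80%: it gives 51.3% two-sided and 63.8% one-sided.

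**2. The randomised comparison: 60 v 60, unadjusted.** SE = 1.2 × √(2/60) = 0.219, df 118. The documents do not say how much of the 24-week gain is reached after 12 weeks on drug, so that share is varied:

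| Share of the 0.44 gained by the 12-week arm (assumed) | Difference | Noncentrality | Power |
|---|---|---|---|
| none | 0.44 | 2.01 | 51.3% |
| one quarter | 0.33 | 1.51 | 32.1% |
| one half | 0.22 | 1.00 | 16.9% |
| three quarters | 0.11 | 0.50 | 7.9% |
| all (plateau by Week 12) | 0 | 0 | 5% |

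For 80% power the trial would need about 118 per arm at a difference of 0.44, or 469 per arm at 0.22.

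**3. Effect of baseline adjustment.** The planned ANCOVA reduces the SD to 1.2 × √(1 − r²), where r is the correlation of change with baseline. The documents give no r. With r assumed to be 0.3 or 0.5 in absolute value, the SD is 1.14 or 1.04. Power is then 55% or 63% at 0.44, and 18% or 21% at 0.22.

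**4. Effect of shared change on the one-arm test.** The documents give no figure, so these shifts are illustrative:

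- No drug effect, shared rise 0.20: noncentrality 0.20/0.155 = 1.29; significant **24.6%** of the time.
- No drug effect, shared rise 0.30: noncentrality 0.30/0.155 = 1.94; significant **47.8%** of the time.
- True gain 0.44, shared decline 0.20: net 0.24, noncentrality 1.55; power falls from 79.8% to **33%**.

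In the between-arm comparison a shared shift cancels.

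**5. The Week 12 test.** SAP Section 10 calls for a change at 12 weeks in the placebo-start arm. At Week 12 that arm has had no ricolinostat and no biopsy is scheduled. Its scheduled change runs from Day 1 to Week 24 and covers 12 weeks of placebo followed by 12 weeks of ricolinostat.

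**The case against.** The strongest reply is that nothing is hidden. The sub-study is labelled exploratory and its power is admitted to be imprecise. The 80% follows directly after the within-arm hypothesis and is worded as an increase. The between-arm ANCOVA is already planned. IENFD lies outside the fixed testing sequence, so its p-values are nominal (SAP Section 8.2), and no passage says that a drug effect will be concluded from the within-arm result. The one directional hint in Protocol Section 7.1, that density may fall with age, would make the one-arm test conservative. All of this stands, and it keeps the point minor. It does not give the lead test a control.

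A second reply also stands: the between-arm contrast is not drug v no drug. Change shared by both arms may be partly real drug effect, and an effect complete by 12 weeks gives no expected difference at Week 24.

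A reader might infer two further faults from the protocol. The first is regression to the mean, because Protocol Section 6.3 looks "at 24 weeks in a subset of patients with painful DPN who have reduced IENFD at baseline" and the Day 1 biopsy would both select patients and serve as the value subtracted. The second is an invalid test, because under Protocol Section 10.3.6 "the test of difference will be based on the significance level of the intercept term in the model", which with uncentred baseline would estimate change at zero density. Neither is supported as a main point. The SAP governs where the documents differ (SAP Section 1). Its objective in Section 2.4 omits the reduced-density restriction, Section 10 applies no density filter, and a t-test replaces the intercept test. Protocol Section 7.1 sets no density threshold for entry, and Section 10.3.6 does not say that baseline is uncentred.

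**Conclusion.** The concern holds as a minor point. The lead IENFD test cannot separate drug effect from shared change, and the 80% covers that test only. The randomised comparison has about 51% power at best unadjusted, or about 55–63% with baseline adjustment under the assumed correlations. It falls towards 5% as the 12-week arm catches up.

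Two stronger readings should be resisted. It is tempting to say that the stated power is wrong; it is correct for the hypothesis it follows. It is also tempting to quote 17–51% as the power range of the randomised comparison. Those figures are for an unadjusted test and assume that the 12-week arm gains between half and none of the effect, so they are neither a floor nor a ceiling.

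The conclusion rests on 1.2 being the SD of change, 60 evaluable patients per arm and a two-sided 0.05 level. The shared-change figures are illustrations, not estimates. The Week 12 contradiction in SAP Section 10 rests on no assumption and needs correction in any case. The primary and key secondary results are unaffected.

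**What to change.** 1. In Protocol Sections 7.1 and 10.3.6 and SAP Section 10, make the already planned between-arm ANCOVA the lead inferential IENFD analysis. Name its estimand as 24 v 12 weeks of ricolinostat, and state that a null result does not rule out an effect already reached by 12 weeks.
2. Report the two within-arm changes with 95% confidence intervals as descriptive, not as evidence of a drug effect.
3. Remove the Week 12 IENFD analysis from SAP Section 10. Describe the second group's change as Day 1 to Week 24, covering 12 weeks of placebo then 12 weeks of ricolinostat.
4. State that the 80% applies only to the within-arm test, and give the randomised comparison's power with its assumptions, as tabulated above.
5. While editing, align the protocol's reduced-density objective and endpoint (Section 6.3 and the synopsis) and its intercept test (Section 10.3.6) with the SAP.

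The cost is wording only: no extra biopsies, patients or models. The downside is a less favourable power statement and the loss of the within-arm p-value as evidence of effect.
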